Exploratory Study on Effect of Whitening Agent with Emulsion Gel in Xerostomic Population

Principal Investigator: [name], DMD, MS

Co-Investigators: [name], DMD, PhD

Study Coordinators:

[name], AS, CDA, CCRP

[name], BS, CCRP

[name], RDH [name]

Study Location: Tufts University School of Dental Medicine

[name]

Sponsor: Procter & Gamble

Protocol Version Date: 4/14/2023

Exploratory Study on Effect of Whitening Agent with Emulsion Gel in Xerostomic Population [name], DMD, MS

I) Introduction

A) Aim/Hypothesis/Objective

Objectives:

- Primary aim: To see a reduction in the self-reported subjective perception of dryness in the oral cavity.
- Secondary aims: To measure self-reported sensitivity of the teeth, self-reported
 perception of teeth whiteness, and objective measurement of improvement of saliva
 production.

II) Background and Rationale

Xerostomia, is a subjective sensation of dryness of the mouth, which may have a significant effect in a persons quality of life. The sensation of dryness of the mouth may be caused by autoimmune diseases which attack the saliva producing glands irreversibly e.g., salivary glands, or the sensation of dryness could be caused by therapeutic radiation, which can destroy the salivary glands at the genetic level and impede their functions. Additionally, there are more than 700 medications including antihypertensives, anti-anxiety agents, psychiatric remedies, and antihistamines that can effect neural transmission. Neural transmission is when the neuro transmission is hindered reversibly leading to the salivary hypofunction that results in dry mouth. It is estimated that 12-47% of the elderly and 10-19.3% in their early 30's suffer from dry mouth (6)(7). In a study, it was found that the prevalence of xerostomia was 10.0% (with no apparent gender difference) among 32-year-olds and was significantly higher among those taking antidepressants (odds ratio =4.7) (5). At risk groups may present much higher (60+%) rates of xerostomia. A systemic literature review suggests a prevalence of 27 –32% of the medicated population suffer from xerostomia as a side effect (7).

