- The study team may terminate subjects if they no longer fulfill inclusion criteria, if an exclusion criterion is met, or if they do not show up for scheduled study visits.
- Subjects who experience an unanticipated adverse drug effect will be withdrawn from the study.
- Subjects unable to complete the study procedures due to a medical condition such as dry mouth and sensitivity conditions that result in the inability to capture meaningful data during the study procedures.
- Subjects may choose to withdraw from the study at any time.

Subjects may remain patients of TUSDM if they decide to withdraw from the study or are withdrawn by the study team.

If during the course of their participation in the study, a subject chooses to withdraw or is withdrawn by the research team, any data that has been

collected will not be included in the analysis and the subject will be asked to return any leftover whitening gel and the diary. The subject is able to keep the toothpaste and toothbrush.

Subjects will not be able to partially withdrawal from study intervention and just be involved with continued data collection.

The Principal Investigator will determine whether subjects (either withdrawn subjects or subjects completing the study) are in need of additional treatment and/or follow-up observation as a result of participation in this trial and will refer them to their primary care provider for further care. Subjects and/or their insurance will be responsible for the cost of any standard of care follow-up visits or additional treatment that is not part of this study.

4) Vulnerable Populations

Transgender subjects will be recruited as part of this study. All subjects will be asked on the Medical/Dental History Form to identify their sex, to which they will answer however they choose. They will not be sought out or targeted for participation and will not be discriminated against as a result of their sexual orientation/gender identity. The subjects will not be asked to disclose if they are transgender or not on the Medical/Dental History Form.

Cognitively impaired adults and pregnant adults will not be enrolled in this study. There would be no direct benefits to these specific vulnerable populations by enrolling them. Pregnancy will be determined through self-reporting.

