Non-English speakers will be excluded from the study because the study team does not have validated questionnaires developed in multiple languages. The study team also does not have the resources to translate the take home diary or manufacturer's

instructions. In addition, the visual demonstration of the application of the study product will not be able to be effectively translated using the Interpreter Machine available at TUSDM. There are no physical translators available at TUSDM to assist in translating the visual demonstration. There are no direct benefits to this population by participating in this study.

E) Assessment

1) Risk

The standard risk associated with teeth whitening products include causing gum irritation, gum or teeth bleaching, teeth sensitivity, and irritation of the oral mucosa (cheeks, lips, tongue). In addition, there is a risk of irritation or whitening from contact with skin from using this study product. Subjects may also feel discomfort when they abstain eating or drinking before the study visit.

There is the risk of loss of confidentiality to the subject by participating in this study. This risk will be kept to a minimum by following procedures listed under confidentiality section.

2) Benefits

There is no direct medical benefit to the subject for participation in this study. However, the results of the study will help better understand whether the application of hydrophobic emulsion containing agents have a beneficial effect in alleviating subjective sensation of mouth dryness along with teeth whitening in a Xerostomic population. The results of this study will help in understanding the contributing factors that alleviate dry mouth and increase esthetics through whitening of teeth.

3) Alternatives

Patients may choose not to participate in the study and to receive the standard of care treatment for dry mouth at TUSDM at normal clinic fees.

F) Study Procedures

Visit 1 (1-1.5 hours) Screening/ Baseline (Day 0)

- 1. Subject will be called 1-2 days before their appointment to confirm that in order to participate, they must:
 - a. Not consume alcohol for 24 hours prior to their visit.
 - b. Not brush their teeth for 1.5 hours prior to their visit.
 - c. Not have had anything to eat or drink (including chewing gum or eating candy) for 1.5 hours prior to their visit). Water is acceptable to drink up to 1 hour prior to the study visit.
 - d. Not smoke 1.5 hours prior to their visit.

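### Subjects who leave the gel are barred from further data collection, so the one-week dryness, sensitivity and saliva results may come from a group selected on outcome

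*Combined protocol and SAP*

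**What the plan says.** All references are to the Combined protocol and SAP.

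- **The bar (III.D.3, Subject Withdrawal/Termination Criteria).** "Subjects will not be able to partially withdrawal from study intervention and just be involved with continued data collection".
- **Data already in hand (paragraph just above it).** For a subject who withdraws or is withdrawn, any data already "collected will not be included in the analysis and the subject will be asked to return any leftover whitening gel and the diary".
- **Ways out (same section).** "Subjects may choose to withdraw from the study at any time". "Subjects who experience an unanticipated adverse drug effect will be withdrawn from the study". The list also names "Subjects unable to complete the study procedures due to a medical condition such as dry mouth and sensitivity conditions", where these prevent meaningful data from being captured.
- **Product risks (III.E.1).** "The standard risk associated with teeth whitening products include causing gum irritation, gum or teeth bleaching, teeth sensitivity, and irritation of the oral mucosa".
- **Aims (I.A).** Self-reported dryness is primary. Self-reported tooth sensitivity and measured saliva production are among the secondary aims.
- **Follow-up (III.F and the schedule table).** There is one post-baseline visit, Visit 2, at 7 days with a window of 2 days either way. It has the only oral exam, questionnaire and saliva collection after Visit 1.
- **Analysis (III.B).** First and final visits are compared with a Student t-test. There is no control group, no blinding, no stated missing-data method and no defined analysis set.
- **Safety (III.G.1).** Adverse events go into source documents and case report forms.

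**The concern.** The rule ties measurement to staying on the intervention. The conditions under study (tooth sensitivity and unrelieved dryness) are also plausible reasons for leaving, and III.D.3 itself names dry mouth and sensitivity conditions among the grounds for withdrawal. Missing Visit 2 values may therefore depend on the outcome.

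In a randomised trial a comparison arm might reveal some of this. Here the only evidence of a one-week effect is the within-subject change among those who return, and nothing in the analysis plan would show or correct the selection. Screening up to 100 people to cover dropouts and screen failures can restore numbers, but it cannot restore the outcomes of those who left. In a one-week study, values not collected at the time cannot be recovered later.

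**Working it through.** **1. The plan's own figure.** III.B gives 25 subjects as sufficient, but states no alpha, sidedness, power, effect or SD, so the 25 cannot be reproduced. Solving backwards with a noncentral-t paired test at two-sided 0.05, 25 pairs detect a standardised change of 0.584 at 80% power or 0.676 at 90%. This shows only that a handful of subjects carries weight. The fix leaves the 25 unchanged.

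**2. Does anything else restore Visit 2 measures?** The visit procedures, schedule table, safety section and withdrawal section contain no exit visit, no later contact for outcome data and no analysis of all treated subjects.

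**3. Formula for the distortion.** Let d be the fraction who stop, C the mean change in continuers and S the mean change that stoppers would show at Visit 2. The reported mean is C and the all-subject mean is (1 − d)C + dS, so

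reported − all = d × (C − S).

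**4. Illustration.** Everything here is assumed: 25 starters, a 0–10 VAS, a sensitivity rise of 0.3 in continuers and 3.0 in stoppers, and dryness relief of 2.0 in continuers and 0 in stoppers.

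| Stoppers of 25 | Sensitivity rise, all 25 (reported: 0.30) | Dryness relief, all 25 (reported: 2.0) |
|---|---|---|
| 2 | (2×3.0 + 23×0.3)/25 = 0.516 | 23×2.0/25 = 1.84 |
| 4 | (4×3.0 + 21×0.3)/25 = 0.732 | 21×2.0/25 = 1.68 |
| 5 | (5×3.0 + 20×0.3)/25 = 0.840 | 20×2.0/25 = 1.60 |

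Varying the dryness assumptions gives a range. At 5% stopping with S = 0, the overstatement is 0.05 × 2.0 = 0.1 points. At 30% stopping with stoppers worse by 1 point, it is 0.30 × (2.0 + 1.0) = 0.9 points.

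**5. False-positive risk.** This was simulated with 25 starters, no true mean change, normally distributed changes, a two-sided paired t-test at 0.05 and 20,000 runs per case.

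| Subjects lost | The worst changes are lost | Stopping correlates 0.5 with change |
|---|---|---|
| 1 | about 8% | about 6% |
| 2 | about 15% | about 7% |
| 5 | about 46% | about 13% |

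The middle column is an extreme case. The right-hand column represents a looser link between stopping and outcome.

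**6. What can reverse the sign.** The formula changes sign if those who leave did better than those who stay. III.D.3 allows termination of subjects who no longer meet the inclusion criteria, and Visit 2 step 3 rechecks this. Those criteria include a dryness score of 5 or more and low unstimulated flow, so improvers could also be removed. In addition, if a stopper's sensitivity had eased back to the continuers' level by Visit 2 (S = C), the distortion in the Visit 2 score is zero.

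**The case against.** The best defence is that the study is exploratory and asks what happens after one week of use, so values taken off the product answer a different question. That has some force, and it is why an analysis limited to subjects who stayed on the gel should be kept as supportive. It does not justify leaving the other values uncollected, because the protocol nowhere defines its population as those who stayed on the gel.

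Four stronger readings are tempting, but the documents do not support them.

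- *A reader might infer that nothing is measured in subjects who leave.* Adverse events, defined to include symptoms and abnormal exam findings, are still recorded (III.G.1). Visit 1 measures are taken, though later excluded, and the diary is called back. What is lost is the Visit 2 questionnaire, saliva collection and exam.
- *A reader might infer that results come only from those who tolerated the gel.* Home use has a ceiling of four applications a day and no minimum, and withdrawal for non-compliance is discretionary. A subject who cut back because of sensitivity could still attend Visit 2 and be analysed.
- *A reader might infer that the results certainly flatter the product.* The possible removal of improvers at Visit 2 leaves the net direction open, and every magnitude above is assumed.
- *A reader might infer a contradiction with the follow-up duty:* "The Principal Investigator will determine whether subjects (either withdrawn subjects or subjects completing the study) are in need of additional treatment and/or follow-up observation". That sentence goes on to provide for referral to the primary care provider, so the duty does not depend on the Visit 2 research exam. The lack of a scheduled exit exam is a gap, not a conflict.

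**Conclusion.** The concern holds in a limited form. The protocol expressly closes Visit 2 measurement to anyone who leaves the intervention, and no other section reopens it. The one-week dryness, sensitivity and flow comparisons can therefore be selected on outcome, with no control arm or missing-data method to expose it. If stopping is driven by intolerance or lack of relief, the expected direction is understated sensitivity and overstated relief.

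The size cannot be derived from the documents, which give no stopping rate, effect or SD. On the assumed values, the overstatement of dryness relief runs from 0.1 to 0.9 VAS points for 5% to 30% stopping. The sensitivity figures further assume that the rise persists to Visit 2 after the gel is stopped. The rule should be changed before enrolment because the repair is cheap and the lost data are not recoverable.

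**What to change.** Separate stopping the gel from withdrawing consent for data collection.

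1. Replace the sentence barring partial withdrawal with: *A subject who stops the gel, other than by withdrawing consent, will be asked to attend Visit 2 in its window for the oral exam, adverse event review, pre-product questionnaire and Saliva Collection 1, without the in-clinic application.*
2. Amend the data-exclusion rule in the paragraph above it, so that these subjects' Visit 1 and Visit 2 pre-product values enter the Visit 1 to Visit 2 comparison. Without this the new values would be collected and then discarded. Present the analysis limited to subjects who stayed on the gel as supportive.
3. Reconcile "Subjects who experience an unanticipated adverse drug effect will be withdrawn from the study" with the new wording, so that the text distinguishes leaving the gel from leaving the study.
4. Report adverse events for all subjects who applied the gel at least once.

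No change to when a subject stops the gel is proposed.

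**Cost.** Protocol and consent wording, and the Visit 2 payment for those who stop: $75 each, so 5 × $75 = $375 if five stop. The compensation text (III.H.4) makes the full $150 conditional on not being withdrawn and needs the same distinction. The visit, staff and forms are already planned. The estimate will include some subjects off product, so apparent relief may be slightly smaller.

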The product being used is a commercially available product, known as "Crest Whitening Emulsions", will be used as the investigative product. There will be no active control group. This is not the first time P&G whitening gel will be used in humans. We do believe this is the first study investigating dry mouth sensation from using a whitening gel.

- III) Research Plan
 - A) Experimental Design

This will be a single center, two visit study investigating the effectiveness of dryness in the oral cavity, whiteness of teeth, and teeth sensitivity after one week's use of whitening agent.

B) Sample Size and Statistical Analysis

Sample size

This is a single site study. All study-related procedures will take place at TUSDM. Based on our preliminary data from a previous study, we anticipate 25 subjects will be needed to achieve the necessary statistical power required to observe expected differences in relief of dryness in the oral cavity. Because we anticipate the potential of many screen failures due to the VAS scale and saliva production requirements outlined in the exclusion/inclusion criteria section, we will screen/enroll a total of 100 subjects to conservatively account for potential dropouts or screening failures.

Statistical analysis

The subjects will be asked to complete one questionnaire each visit. Completing the first part before the application of the study product, and completing the second part after the application of the study product, as directed on the questionnaire. The self-reported scores from the visual analogue scales (VAS) will be considered on the first and final visit. The salivary flow before and after the application of the product, Pre & Post-Product Use Dry Mouth & Sensitivity Questionnaire before and after the product application will be compared using a student -t test method. The same method will be used to make comparisons of these gathered data points between the first and final visits.

Randomization

This will be an open label study; thus no randomization plan is necessary.

Blinding

There will be no blinding for this study.

C) Products

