The investigational product to be used in this study is manufactured by P&G and called, "Crest Whitening Emulsions". The amount of each dose should be enough to cover the entire tip of the whitening wand, approximately ½ a tsp. The use of the study product in this study will be for what they are approved for. Per the manufacturer's instructions, study subjects will be asked to apply the study product up to 4 times a day.

Procter and Gamble will be supplying the study product gel to the study team. IDS will not be involved in this study.

The investigative product to be used in this study is a hydrophobic emulsion containing agent (a teeth whitening gel with emulsification gel). It contains:

Petrolatum, Water, Hydrogen Peroxide, Flavor, Sucralose, Sorbitan Palmitate

D) Subject Characteristics

- 1) Inclusion Criteria
 - At least 18 years of age.
 - The inability to produce more than < 0.18mL/min of unstimulated saliva.
 - Score of 5 or more on question 1 of the VAS dry mouth scale (How severe is your dryness right now?), evaluated in the Pre-Product Use Dry Mouth & Sensitivity Questionnaire .
 - Evidence of currently taking Xerostomia-inducing medication such as, antihypertensives, anti-anxiety agents, psychiatric remedies, antihistamines.
 - Subject not currently using any teeth whitening or desensitizing products
 that contain potassium nitrate such as Sensodyne or Pronamel.
 - Subject willing to comply with the study regimen and products.

2) Exclusion Criteria

- Subjects who are currently pregnant (self-reported).
- Subjects able to produce more than 0.18mL/min of unstimulated saliva

- Subjects that have ever received therapeutic radiation in the head and neck area.
- Subjects with a diagnosis of conditions that would affect salivary flow such as Sjogren's Syndrome.
- Subjects with a condition the investigator believes not suitable for the study such as autoimmune diseases that impact salivary flow.
- Subjects that currently use whitening toothpaste, desensitizing toothpaste, or any other products causing similar results.
- Subjects currently participating in any other research studies.
- Subject unable to provide consent (ex. Cognitively impaired adults).
- Non-English speaking

3) Subject Withdrawal/Termination Criteria

- Subjects who do not comply with the study procedures, such as use of teeth whitening products, may be withdrawn from the study.

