- The subjects will be asked to read the informed consent form (ICF). Subjects will
 be given ample time to have any questions answered. If a subject decides to
 participate, he or she will be asked to sign the ICF. A copy of the ICF will be given
 to the subject.
- 3. Subject will be asked to complete demographic information and a medical history.
- 4. An oral exam, including evaluation of oral cavity, soft and hard tissues, will be completed following standard of care procedures in US dentistry using a mouth mirror and dental explorer.
- 5. Subject medications with potential side effects being dry mouth will be verified using the Physician's Reference Desk.
- 6. Saliva Collection 1 (pre-product application): Saliva will be collected by asking subjects to do nothing but drool into a pre-weighed vial for 5 minutes (referred to as the Drooling Method). The post collection weight will be subtracted from the pre-weight to determine the flow rate. The saliva samples will be discarded after they are weighed.
- A paper questionnaire will be given to subject to complete before application of study product and after application of study product. Questionnaire includes Visual Analogue Scale (VAS) questionnaire on dry mouth, quantity of saliva, and perceived sensitivity of teeth.

- 8. Inclusion/exclusion criteria will be evaluated and eligibility for the study will be determined.
- 9. Demonstration and application of study product:
 - a. A visual and oral demonstration of application of the whitening gel will be performed by a study team member. The script for the demonstration will be the one provided in the information packet in each study product box so the subject can bring the instructions home. The study team member will mimic the necessary steps to properly apply the gel, without using the product. The study team member will then have the subject complete the steps while applying the gel to their own teeth. Subjects will then be asked to sit for 5 minutes to let the gel set on their teeth.
- 10. Saliva Collection 2 (post-product application): Saliva will be collected using the same Drooling Method as Saliva Collection 1. The saliva samples will be discarded after they are weighed.

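### The saliva flow rule subtracts in the wrong order and omits the conversion from grams per 5 minutes to mL/min that the 0.18 mL/min entry limit requires

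*Combined protocol and SAP*

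**What the plan says.** All references are to the combined protocol and SAP.

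- **Calculation.** III.F Study Procedures, step 6 of Visit 1 and again step 6 of Visit 2: "The post collection weight will be subtracted from the pre-weight to determine the flow rate". Each collection lasts 5 minutes, into a vial weighed beforehand.
- **Post-product collections.** Visit 1, step 10: "Saliva will be collected using the same Drooling Method as Saliva Collection 1". Visit 2, step 9 is to the same effect. Neither restates the calculation, so the step 6 sentence governs all four collections.
- **Entry limit.** III.D.1 Inclusion Criteria: "The inability to produce more than < 0.18mL/min of unstimulated saliva". III.D.2 Exclusion Criteria: "Subjects able to produce more than 0.18mL/min of unstimulated saliva". Eligibility is decided at Visit 1, step 8, after the first collection.
- **Expected effect of the limit.** III.B, Sample size: "we anticipate the potential of many screen failures due to the VAS scale and saliva production requirements".
- **Use as an outcome.** Section I.A lists among the secondary aims an "objective measurement of improvement of saliva" production. III.B, Statistical analysis, says that flow before and after application "will be compared using a student -t test method", and applies the same method between visits. It does not say whether the test is paired, or one- or two-sided.

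**The concern.** The step 6 sentence is the only rule for turning vial weights into a flow, and it has two defects.

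1. **Order.** Subtracting the post-collection weight from the pre-weight gives pre minus post. A vial gains weight when saliva enters it, so the result is zero (no saliva) or negative. No section gives the opposite order.
2. **Units.** The sentence calls a weight difference a flow rate. It neither divides by the 5 collection minutes nor converts grams to millilitres, while the limit is in mL/min.

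The inclusion criterion adds a third difficulty: it places both a more-than phrase and a less-than sign before 0.18, so it cannot be used to settle how the limit works.

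Two things depend on the number: who enters the study, and the direction of the only objectively measured secondary outcome. The primary aim, self-reported dryness, is not computed from it, although the entry limit affects who contributes to that analysis.

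**Working it through.** **Inputs from the protocol.** Collection time 5 min (III.F, step 6, both visits); limit 0.18 mL/min (III.D.1 and III.D.2); subtraction order as worded in step 6.

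**Assumption not in the protocol.** Saliva density d = 1 g/mL. The sign of every result is the same for any positive d. The weights below scale in proportion to d, and the implied limit in step 4 is 0.036/d.

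The plan gives no worked flow value, so there is no figure of its own to reproduce.

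**Step 1: the limit as a weight.** 0.18 mL/min x 5 min x 1 g/mL = 0.90 g gained per collection.

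**Step 2: three readings of the rule, for assumed true flows.**

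- A, order as worded: (pre - post)/5. The division is supplied here so that only the order is being tested.
- B, corrected: (post - pre)/5.
- C, order corrected but not divided: post - pre, in grams, compared directly with 0.18.

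A subject is excluded if the value is above 0.18.

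| True flow (mL/min) | Gain (g) | A | Excluded | B | Excluded | C | Excluded |
|---|---|---|---|---|---|---|---|
| 0 | 0 | 0 | no | 0 | no | 0 | no |
| 0.05 | 0.25 | -0.05 | no | 0.05 | no | 0.25 | yes |
| 0.10 | 0.50 | -0.10 | no | 0.10 | no | 0.50 | yes |
| 0.18 | 0.90 | -0.18 | no | 0.18 | no | 0.90 | yes |
| 0.19 | 0.95 | -0.19 | no | 0.19 | yes | 0.95 | yes |
| 0.30 | 1.50 | -0.30 | no | 0.30 | yes | 1.50 | yes |
| 0.50 | 2.50 | -0.50 | no | 0.50 | yes | 2.50 | yes |
| 1.0 | 5.0 | -1.0 | no | 1.0 | yes | 5.0 | yes |

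Under A the exclusion criterion removes nobody. Leaving out the division under A makes the negative values five times larger and changes no decision. Only B separates subjects at 0.18 mL/min.

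**Step 3: direction of change.** For a rise from 0.10 to 0.15 mL/min, reading A gives (-0.15) - (-0.10) = -0.05 and reading B gives 0.15 - 0.10 = +0.05. Multiplying every flow by -1 changes the sign of a t statistic and nothing else, whether the test is paired or unpaired. In a simulated set of 25 pairs (invented values, for illustration only), t went from +2.22 to -2.22 and the two-sided p stayed at 0.036. That p-value resembles the limit in step 4 by coincidence.

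**Step 4: implied limit under C.** A gain of 0.18 g in 5 min is 0.18/5 = 0.036 mL/min, one fifth of the stated limit. Subjects with true flow above 0.036 and up to 0.18 mL/min would be turned away although the exclusion criterion does not apply to them; the subject at 0.05 mL/min (0.25 g) is one.

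**Step 5: the two criteria side by side.** If the less-than sign in the inclusion criterion is a stray character, flow must not exceed 0.18 and the two criteria are exact complements. If the sign is the intended part, flow must be below 0.18, and a subject at exactly 0.18 is neither included nor excluded. The text does not show which is meant.

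**The case against.** The strongest case on the other side is that this is a drafting slip with no realistic route to harm. The protocol treats flow as positive throughout: the limit is positive, many screen failures are expected partly because of it, and the aim is improvement. A rule that excludes nobody contradicts that expectation, so the intended order is clear. A negative flow would show at the first weighing, and the raw weights would allow it to be corrected. The collection time and the unit are both stated, so division by 5 is implied by the idea of a rate; nothing says that grams would be compared with 0.18. The exclusion criterion is readable on its own, and the Visit 2 sentence may be one slip copied.

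Most of this stands. A reader might infer that every screened subject will pass the saliva criterion and that the saliva result will be reported with the wrong sign. The documents do not support that; these are consequences of literal application only. It would also be too strong to say that every flow comes out negative, since no saliva gives 0, or that significance is affected in a two-sided test. The readings that exclude nobody and that exclude too many cannot both occur.

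Two things survive. The sentence is the only calculation rule and cannot, as written, yield the quantity the protocol needs. And the implied division is not written anywhere: unlike a negative flow, an undivided gain is a positive, plausible-looking number, and the extra screen failures it would cause could pass as the many already expected.

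**Conclusion.** The point holds as an error in an operative calculation rule, of modest consequence. The order of subtraction is reversed at both visits and the step from grams per 5-minute collection to mL/min is missing; both are certain from the text.

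The effect is conditional. Applied literally, flows are zero or negative, the exclusion limit removes nobody, and the direction of change reverses with its size and two-sided p unchanged. This would probably be caught. If the sign is put right but the division is not made, and grams are compared with 0.18, the limit becomes 0.036 mL/min instead of 0.18. That figure assumes 1 g = 1 mL. Nothing shows that either miscalculation would in fact be made.

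The inclusion wording leaves one value open, exactly 0.18 mL/min, and the documents do not settle it.

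**What to change.** 1. In III.F, Visit 1 step 6 and Visit 2 step 6, replace the calculation sentence with: flow (mL/min) = (post-collection vial weight - pre-collection vial weight, in g) / 5 min, taking saliva density as 1 g/mL.
2. In Visit 1 step 10 and Visit 2 step 9, say that the same formula applies, so that all four collections are covered.
3. Reconcile the saliva criteria in III.D.1 and III.D.2 so that each is the exact complement of the other. Whether exactly 0.18 mL/min qualifies is for the sponsor to decide and state.

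The cost is a few edited sentences submitted as a protocol amendment. No new data, procedure or visit is needed.
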